3.2 Exclusion Criteria

- 3.21 Any of the following because this study involves an agent that has known genotoxic, mutagenic and teratogenic effects:
 - Pregnant women
 - Nursing women
 - Men or women of childbearing potential who are unwilling to employ adequate contraception
- 3.22 Chemotherapy/systemic therapy, radiotherapy, immunotherapy or surgery ≤ 21 days prior to registration or kinase inhibitor therapy ≤ 14 days prior to registration or failure to recover from toxicities (to Grade 1 or below) from treatment.

NOTE: Concurrent therapy with octreotide is allowed providing that tumor progression on this therapy has been demonstrated. Concurrent therapy with bisphosphonates (e.g. zoledronic acid) or denosumab is also allowed.

NOTE: An unlimited number of prior chemotherapeutic or biologic therapies for malignant pheochromocytoma or paraganglioma is permitted. This includes prior anti-angiogenesis therapies such as tyrosine kinase inhibitors.
- 3.23 Active or uncontrolled intercurrent illness including, but not limited to, ongoing or active infection, symptomatic congestive heart failure, unstable angina pectoris, cardiac arrhythmia, or psychiatric illness/social situations that would limit compliance with study requirements.
- 3.24 Receiving any other investigational agent
- 3.25 Current use of warfarin for any reason.

NOTE: If patient can be safely transitioned to another anticoagulant, they may be eligible provided other criteria are satisfied.
- 3.26 Any of the following:
 - QTc prolongation (defined as a QTc interval ≥ 500 msec)
 - LVEF $<$ institutional LLN
 - frequent ventricular ectopy
 - evidence of ongoing myocardial ischemia
- 3.27 Receiving any medications or substances with risk of torsades de pointes (see [Appendix V](#) for partial list).

NOTE: Medications or substances with known Risk of Torsades de Pointes are prohibited. Consult pharmacist for review if needed.
- 3.28 Known active and/or untreated brain metastases.
- 3.29a Known severe allergic or other prohibitive reactions to other tyrosine kinase inhibitors (TKI).
- 3.29b Prior treatment with lenvatinib.
- 3.29c Any of the following conditions:
 - Active peptic ulcer disease
 - Inflammatory bowel disease (e.g., ulcerative colitis, Crohn's disease) or other

gastrointestinal conditions which increase the risk of perforation

- History of new abdominal fistula, gastrointestinal perforation or intra-abdominal abscess ≤ 84 days prior to registration
NOTE: Enrollment of patients with chronic/canalized fistulous tracts (present for >84 days) is allowed.
- Serious or non-healing wound, ulcer, or bone fracture
- History of familial QTc prolongation syndrome

3.29d Any of the following conditions ≤ 6 months prior to registration:

- Cerebrovascular accident (CVA) or transient ischemic attack (TIA)
- Serious or unstable cardiac arrhythmia
- Admission for unstable angina or Myocardial infarction
- Cardiac angioplasty or stenting
- Coronary artery bypass graft surgery
- Pulmonary embolism, untreated deep venous thrombosis (DVT) or DVT which has been treated with therapeutic anticoagulation ≤ 30 days
- Arterial thrombosis
- Symptomatic peripheral vascular disease

3.29e Other active malignancy ≤ 2 years prior to registration.

EXCEPTIONS: Non-melanotic skin cancer or carcinoma-in-situ of the cervix.

NOTE: If there is a history of prior malignancy, they must not be receiving other specific treatment for their cancer.

NOTE: Adjuvant anti-estrogen/hormonal therapy for breast cancer is allowed

4.0 STUDY CALENDAR

4.1 Test Schedule

Tests and procedures ¹				Active Treatment				End of Treatment	
	≤28 days prior to registration	≤14 days prior to registration	≤7 days prior to registration	Cycle 1			Prior to Day 1 of subsequent cycles ³	Every 2 months	
				D1	D3	D10 ²			
Tests and procedures ¹	Window:						±3 days	±7 days	±14 days
Clinical Procedures									
Vital signs, history (including personal/family history for prolonged QTc) and exam, weight, PS		X		X	X	X	X		X
Height		X							
Review of concurrent medications ⁴		X					X		
Pregnancy test ⁵			X						
Blood pressure monitoring ⁶		X		X	X	X	X		
Adverse event assessment		X		X	X	X	X		X
Consultation with endocrinologist, cardiologist, or nephrologist for blood pressure management		X					X		
Hematology: CBC/diff ⁷		X					X		X
Chemistry Panel ⁸		X					X		X
TSH		X					X		
24 hr urine catecholamine and metanephhrines		X					X		
Plasma fractionated metanephhrines		X					X		
Urinalysis ⁹		X					X		
Urine protein/creatinine ratio		X					X		
Genetic counseling and testing at discretion of patient and counselor ¹⁰	X								

¹ All tests and procedures are clinically indicated, unless noted with an R to indicate funding by research

² May be omitted at discretion of treating provider and replaced with telephone call contact.

³ If patient is tolerating treatment well, return visits may be performed over the phone for non-imaging cycles (starting with cycle 3, 5, 7 etc.). During these phone visits the patient status, treatment information, and Adverse Event Assessments must be assessed and recorded. Labs may be done locally and transmitted to Mayo Clinic.

⁴ Concurrent/concomitant medications are reviewed every cycle. Only requested medications are recorded in the study case report forms.

⁵ For women of childbearing potential only. Must be done ≤7 days prior to registration

⁶ Note: 1) daily monitoring of blood pressure is REQUIRED and must be recorded in patient diaries throughout the entire duration of therapy; 2) any systolic BP >150 mm Hg and/or diastolic BP >100 mm Hg must be brought to the attention of treating provider <24h after noted; 3) any systolic BP >200 mm Hg and/or diastolic BP >110 mm HG should prompt immediate cessation of lenvatinib therapy maintained until remediation to <150 mm Hg systolic is accomplished.

⁷ Must include: hemoglobin (hgb), MCV, leukocyte count, neutrophils (ANC), monocyte count, lymphocyte count, and platelet count (PLT)

⁸ AST, alk phos, total bilirubin (direct if TBili is elevated), creatinine (and calculated creatinine clearance), albumin, glucose, calcium (Ca), sodium (Na), potassium (K), magnesium (Mg), phosphorus (P), uric acid, LDH,

⁹ Urinalysis for protein, glucose, blood

¹⁰ Only if not performed previously (optional); can be performed anytime during study. Testing should include SDHD, SDHB, RET, VHL, neurofibromatosis type-1 genes.

Tests and procedures ¹	Window:				Active Treatment			End of Treatment
		≤28 days prior to registration	≤14 days prior to registration	≤7 days prior to registration	Cycle 1		Prior to Day 1 of subsequent cycles ³	
		D1	D3	D10 ²	Every 2 months			
PET-CT or CT (Chest, Abdomen and pelvis), or MRI abdomen/MRI neck, if needed	X						X	X ¹¹
ECG		X					X ¹²	
2D-ECHO	X							
Blood or Tissue- Analysis performed by Research Lab								
Optional tissue sample for correlatives (see Section 17.0) ¹³				X				
Optional research blood will be collected under IRB 13-005838 ¹⁴		X						
Quality of Life assessment								
Patient Questionnaire Booklet: EQ-5D-5L/FACT-G				X ¹⁵			X	

Cycle = 28 days

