Renal and urinary disorders	Proteinuria Grade ≥ 3		Grade 3, hold lenvatinib until it resolves to Grade 2 or less and resume at one reduced dose level (see Section 8.33) Grade 4, discontinue lenvatinib and enter event monitoring
Skin and subcutaneous tissue disorders	Palmoplantar erythrodysesthesia Grade ≥ 2		Grade 2, hold lenvatinib until it resolves to Grade 1 or less and resume at one reduced dose level Grade 3, discontinue lenvatinib and enter event monitoring

CTCAE System/Organ/Class (SOC)	ADVERSE EVENT	AGENT	ACTION**
Skin and subcutaneous tissue disorders	Maculopapular-rash Grade ≥ 2	lenvatinib	Grade 2, hold lenvatinib until it resolves to Grade 1 or less and resume at one reduced dose level Grade 3, discontinue lenvatinib and enter event monitoring
Vascular disorders	Hypertension Grade ≤ 3		Dose adjust and/or hold lenvatinib and continue to manage per Appendix IV ; consultation with expert recommended Grade 4, discontinue lenvatinib and enter event monitoring
Other non-hematologic adverse events (excluding alopecia)	Grade ≥ 3		Grade 3, hold lenvatinib until AE resolves to Grade 1 or less and resume at one reduced dose level Grade 4, discontinue lenvatinib and enter event monitoring

NOTE: If the patient experiences a significant adverse event requiring a dose reduction at the start of the next cycle, then the dose will remain lowered for that entire subsequent cycle. If that cycle is completed with no further adverse events $>$ Grade 2, then the dose may be increased, at the investigator's discretion, one level at a time, in the following cycles.

NOTE: Adverse events requiring a dose-reduction step for any or all drugs beyond the two dose-reduction steps (levels -1 and -2) will be at the discretion of the treating physician, if the decision is made for the patient to be kept on study. These dose reductions must be clearly recorded in reported clinical data.

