Appendix IV Hypertension Management Guidelines

D.1. Guidelines for the management of lenvatinib-Induced Hypertension: Non-secretory tumors

(For secretory tumors please see Section D.2.)

Increases in blood pressure (BP) and cases of hypertension have been associated with many drugs acting on the VEGF pathway. The proposed mechanism for this increase is through inhibition of VEGF-induced peripheral vasodilation. Hypertension following lenvatinib is well documented in clinical trials. With secretory paraganglioma and pheochromocytoma this could be a major toxicity.

NOTE: that hypertension management of secretory tumors is more complex due to the additional risk of hypertension issues in these patients and management is discussed separately below. For example consultation with HTN specialist is required in patients with secretory tumors prior to study initiation.

- While subjects are receiving treatment with lenvatinib, the early initiation of antihypertensive treatment for grade 1 or 2 hypertension to minimize more severe or persistent hypertension is not considered a grade 3 AE.
- Decisions to hold or decrease the lenvatinib dose during treatment must be based on BP readings taken in the clinic by a medical professional.

Recommended Hypertension Monitoring and Management for non-secretory tumors (BP in mmHg)

Grade (CTCAE v4)	Antihypertensive Therapy	Blood Pressure Monitoring	Lenvatinib Dose Modification
Persistent* Grade 1 Pre-hypertension Systolic 120-139 Diastolic 80-90		Standard	No Change
Persistent Grade 2- Moderate Systolic 140-159 Diastolic 90-99 Protocol-specific guidance supersedes any other management guidelines, including CTCAE v4.	Step 1) Initiate anti-hypertensive treatment (calcium channel blocking agents, e.g. amlodipine, are generally the preferred agents) and if needed, after 24-48 hr Rx, increase dose in stepwise fashion every 24-48 hours until BP is controlled or at max dose of Rx Step 2) If BP still not controlled, add another anti-hypertensive Rx, a LA DHP CCB, ACE1, ARB, or ABB; increase dose of this drug as described in Step 1 Step 3) If BP still not controlled, add 3 rd drug from the list of anti-	BP should be monitored as recommended by the treating physician	No change except as described in Step 4

Recommended Hypertension Monitoring and Management for non-secretory tumors (BP in mmHg)

Grade (CTCAE v4)	Antihypertensive Therapy	Blood Pressure Monitoring	Lenvatinib Dose Modification

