	
hypertensives in Step 2; increase dose of this drug as described in Step 1
 
Step 4) If BP still not controlled, discontinue lenvatinib until BP controlled, then resume
 
NOTE: Stopping or reducing the dose of lenvatinib is expected to cause a decrease in BP.
 
The treating physician should monitor the subject for hypotension and adjust the number and dose of anti-hypertensive medication(s) accordingly
		
Persistent Grade 3 Severe Systolic ≥ 160 Diastolic ≥ 100 Protocol-specific guidance supersedes any other management guidelines, including CTCAE v4	
HOLD lenvatinib until systolic BP ≤ 159 and diastolic BP ≤ 99
 
BP management is identical to that for Grade 2 (see Steps 1-4 above) with 2 major exceptions:
 
1) If systolic BP > 180 or diastolic BP > 110 and the subject is symptomatic: optimal management with intensive IV support in ICU; STOP lenvatinib and notify hospital staff that stopping drug may result in a decrease in BP and
 
2) If systolic BP > 180 or diastolic BP > 110 and the subject is asymptomatic, consideration to initiation of 2 new antihypertensives together should be given in step 1 (and dose escalated appropriately as in step 1).
	
BP should be monitored as recommended by the treating physician unless the subject is symptomatic with systolic BP > 180 or diastolic BP > 110 in which case, monitoring should be intensive
	
HOLD lenvatinib until systolic BP ≤ 159 and diastolic BP ≤ 99. After this, lenvatinib may be re-administered. If BP is still Grade 2, manage as described above for Grade 2 hypertension.
 
In most circumstances, if BP cannot be controlled after an optimal trial of antihypertensive medications, consider either 1 dose reduction of lenvatinib when systolic BP ≤ 159 and diastolic BP ≤ 99 or stopping lenvatinib.
 
HOWEVER, If the subject requires hospitalization for management of symptomatic systolic BP > 180 or diastolic BP > 110,

Recommended Hypertension Monitoring and Management for non-secretory tumors (BP in mmHg)

Grade (CTCAE v4)	Antihypertensive Therapy	Blood Pressure Monitoring	Lenvatinib Dose Modification

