All patients with secretory pheochromocytomas or paragangliomas are required to: 1) be evaluated in consultation, and followed by, a hypertension specialization with experience in the management of hypertension in the setting of catecholamine-secreting tumors (usually an endocrinologist, nephrologist, or a cardiologist), and 2) receive α - and β -adrenergic blockade for at least 7-14 days prior to initiation of lenvatinib (see below for guidelines regarding proper α - and β -blockade). The hypertension specialist of record for each patient should be committed to following the patient during the clinical study on an as needed basis.

Recommended Hypertension Monitoring and Management for Patients with Catecholamine-Secreting Tumors (BP in mmHg) (CTCAE SOC Vascular Disorders/Hypertension)

Grade (CTCAE v4)	Antihypertensive Therapy	Blood Pressure Monitoring	Lenvatinib Dose Modification
Persistent* Grade 1 Pre-hypertension Systolic 120-139 Diastolic 80-90	Standard α - and β -adrenergic blockade	Standard	No Change
Persistent*Grade 2- Moderate Systolic 140-159 Diastolic 90-99 Protocol-specific guidance supersedes any other management guidelines.	Step 1) Advance dose of α -adrenergic blocker until BP is controlled or at max dose of Rx. The β -adrenergic blocker dosage should be advanced for a target heart rate of less than 80 bpm. Step 2) If BP still not controlled, add another anti-hypertensive Rx (usually best a calcium channel blocker such as amlodipine), in conjunction with the patient's identified hypertension specialist, increasing dosage of this drug as described in step 1 or as suggested by patient's identified hypertension specialist. Step 3) If BP is still not controlled, consider either 1 dose reduction of lenvatinib or withholding lenvatinib until BP is better controlled. NOTE: Stopping or reducing the dose of lenvatinib is expected to cause a decrease in BP. The treating physician must therefore monitor the subject for hypotension and adjust the number and dose of antihypertensive medication(s) accordingly	BP should be monitored as recommended by the treating physician and patient's identified hypertension specialist	No change except as described in Step 4

Recommended Hypertension Monitoring and Management for Patients with Catecholamine-Secreting Tumors (BP in mmHg)
(CTCAE SOC Vascular Disorders/Hypertension)

Grade (CTCAE v4)	Antihypertensive Therapy	Blood Pressure Monitoring	Lenvatinib Dose Modification

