Persistent* Grade 3 Severe Systolic ≥ 160 Diastolic ≥ 100 Protocol-specific guidance supersedes any other management guidelines.	HOLD lenvatinib until systolic BP ≤ 159 and diastolic BP ≤ 99 BP management is identical to that for Grade 2 (see steps 1-3 above) with 2 major exceptions: 1) If systolic BP >180 or diastolic BP >110 and the subject is symptomatic: optimal management is with intensive IV support in ICU; STOP lenvatinib and notify hospital staff that stopping lenvatinib may result in a decrease in BP and 2) If systolic BP >180 or diastolic BP >110 and the subject is asymptomatic, Consultation with patient's identified hypertension specialist is required as to the proper medical therapy, addition of additional anti-hypertensive medications and monitoring. NOTE: Stopping or reducing the dose of lenvatinib is expected to cause a decrease in BP. The treating physician should monitor the subject for hypotension and adjust the number and dose of antihypertensive medication(s) accordingly	BP should be monitored as recommended by the treating physician and patient's identified hypertension specialist unless the subject is symptomatic with systolic BP >180 or diastolic BP >110 in which case, monitoring should be intensive.	HOLD lenvatinib until systolic BP ≤ 159 and diastolic BP ≤ 99 . After this, lenvatinib may be re-administered. If BP is still grade 2, manage as described above for grade 2 hypertension. In most circumstances, if BP cannot be controlled after an optimal trial of antihypertensive medications, consider either 1 dose reduction of lenvatinib when systolic BP ≤ 159 and diastolic BP ≤ 99 or stopping lenvatinib. HOWEVER, If the subject requires hospitalization for management of symptomatic systolic BP >180 or diastolic BP >110, permanently discontinue lenvatinib or if BP is controlled to systolic BP ≤ 159 and diastolic BP ≤ 99, consider re-starting lenvatinib at 1 lower dose level after consultation with the study Principal Investigator
Grade 4 Life-threatening consequences of hypertension	Optimal management with intensive IV support in ICU; Contact of patient's identified hypertension specialist. STOP lenvatinib and notify hospital staff that stopping lenvatinib may result in a decrease in BP	Intensive	Permanently discontinue lenvatinib or if systolic BP ≤ 159 and diastolic BP ≤ 99 , consider re-starting lenvatinib at 1 lower dose level after consultation with the study Principal Investigator

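### After a blood pressure above 200 systolic or 110 diastolic, calendar footnote 6 and Appendix IV set different limits for restarting lenvatinib, and two Appendix IV table entries need correcting

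*Combined protocol and SAP*

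**What the plan says.** Section 4.1, footnote 6, sets the stop: any systolic above 200 and/or diastolic above 110 mmHg "should prompt immediate cessation of lenvatinib therapy maintained until remediation to <150 mm Hg systolic is accomplished". Diastolic appears in the trigger but not in the restart condition.

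For hypertension of Grade 3 or below, Section 8.2 gives a different route: "Dose adjust and/or hold lenvatinib and continue to manage per" Appendix IV. That appendix has one table for non-secretory tumours (D.1) and one for secretory tumours (D.2). The Grade 3 rows start at 160 systolic or 100 diastolic, have no upper bound and carry sub-rules for readings above 180 or 110. In D.2 the instruction is "HOLD lenvatinib until systolic BP ≤ 159 and diastolic BP ≤ 99", followed by "After this, lenvatinib may be re-administered. If BP is still grade 2, manage as described above for grade 2 hypertension". D.1 has the same limits and continues "After this, lenvatinib may be re-administered. If BP is still Grade 2, manage as described above for Grade 2 hypertension". In both tables the rule for patients hospitalised with symptomatic pressure above 180 or 110, and the Grade 4 rule, use the same ≤159/≤99 limit. There, the choice is permanent discontinuation or a considered restart one dose level lower after consulting the Principal Investigator.

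Two further entries matter. The Grade 2 lenvatinib cell in D.2 reads "No change except as described in Step 4". Both tables give Grade 1 diastolic as 80-90 and Grade 2 as 90-99.

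**The concern.** After the most extreme readings in the trial, two pages of the same protocol give different conditions for resuming the study drug, and neither refers to the other. A site that goes where Section 8.2 sends it would not learn of the <150 limit. A site that works from the calendar has no diastolic limit at all, although a diastolic above 110 is enough on its own to stop treatment.

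Hypertension is the leading expected toxicity, and Section 1.3 lowers the starting dose to 20 mg because of it. Appendix IV also ends protocol therapy when a hypertension delay exceeds two weeks, so the limit a site applies can bear on whether a patient stays on treatment.

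**Working it through.** No plan figure needs reproducing. The check sets the two restart rules side by side.

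Inputs:
- Footnote 6 (F6): triggered by any systolic >200 and/or diastolic >110; restart when systolic <150.
- Appendix IV (A4), D.1 and D.2: restart when systolic ≤159 and diastolic ≤99. The Grade 3 rows apply to persistent elevation, defined in the table notes as at least two measurements 7 or more days apart.

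For a patient who has had a reading above 200 or 110 and to whom both rules apply:

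| Pressure now | F6 | A4 | Agree? |
|---|---|---|---|
| Systolic <150, diastolic ≤99 | restart | restart | yes |
| Systolic 150-159, diastolic ≤99 (155/95) | hold | restart permitted | no |
| Systolic <150, diastolic ≥100 (145/105) | restart | hold | no |
| Systolic 150-159, diastolic ≥100 | hold | hold | yes |
| Systolic ≥160 | hold | hold | yes |

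The first disagreement spans 159 − 150 + 1 = 10 whole mmHg of systolic pressure. The second exists because footnote 6 has no diastolic condition. At 145/115, for example, 115 > 110 triggers the stop, yet 145 < 150 already meets footnote 6's restart condition. Appendix IV would keep this patient on hold (115 > 99), but its Grade 3 row clearly applies only if the elevation is persistent.

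Precedence: Appendix IV states "Protocol-specific guidance supersedes any other management guidelines, including CTCAE v4". This does not rank the two rules, because both are protocol text.

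Cross-reference: the D.2 Grade 2 row lists Steps 1 to 3, and the D.2 Grade 3 row refers back to steps 1-3. The lenvatinib cell points to Step 4, which exists only in D.1. In D.2 the step that changes lenvatinib is Step 3 (one dose reduction, or withholding).

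Band overlap: {80,…,90} ∩ {90,…,99} = {90}. The systolic bands (120-139, 140-159, ≥160) and the Grade 2/Grade 3 diastolic bands (90-99, ≥100) do not overlap. At a persistent 130/90, Grade 1 means no change to lenvatinib. Grade 2 starts the step-up that can end in a hold (D.1 Step 4) or a reduction or hold (D.2 Step 3). The overlap can therefore affect lenvatinib as well as antihypertensive treatment.

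**The case against.** The best defence is that the two rules mostly address different situations. Footnote 6 covers any reading. The Appendix IV Grade 3 rows cover persistent elevation, sit in tables headed as recommendations, and say only that lenvatinib may be given again. D.1 also ties hold and reduction decisions to clinic readings. Waiting for <150 systolic and ≤99 diastolic satisfies both rules. Readings above 180 or 110 also get special handling: hospitalised symptomatic patients stop, or may be considered for a lower dose after Principal Investigator consultation, and asymptomatic secretory patients need specialist consultation.

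Much of this stands, and it narrows the point. A reader might infer that every extreme reading meets two contradictory rules; the documents do not support that, because a single non-persistent reading falls clearly under footnote 6 alone. But persistent Grade 3 can include readings above 200 or 110, the Grade 4 row is not limited to persistent elevation, and the special handling keeps the same ≤159/≤99 limit. That one course satisfies both rules does not help a site that reads only one of them.

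A reader might also infer that D.1 Step 4 is in error because it offers only a hold, and that control in the Grade 2 steps should be defined as below 140/90. The documents do not support this either. Section 8.2 already allows dose adjustment. The 140/90 figure would be a new clinical threshold taken from the patient call limits in Section 9.72 and Appendix VI. It is stricter on systolic than the <150/<90 entry limit in Section 3.18, and it would hold Grade 2 patients to a tighter target than those recovering from above 200.

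The cross-reference is a small slip, since Step 3 stands in the same row. It still needs correcting.

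**Conclusion.** Wrong as written, as a dosing-safety rule, and minor in extent. Where footnote 6 and Appendix IV both apply, they disagree in two zones: systolic 150-159 with diastolic ≤99, and systolic <150 with diastolic ≥100. Where only footnote 6 applies, it lacks a diastolic restart limit. The Step 4 reference in D.2 and the double listing of diastolic 90 are plain table errors.

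The number of patients affected cannot be derived. A reader might use the 42% rate of grade ≥3 hypertension in Section 1.233 as an estimate. That figure comes from thyroid cancer at 24 mg daily and counts all grade ≥3 events, not readings above 200 or 110. Sample size and the decision rule are unaffected.

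The conclusion assumes that a patient with persistent Grade 3 or Grade 4 hypertension can also have had a reading that triggers footnote 6, which the unbounded Grade 3 range allows. Section 8.2 itself directs discontinuation for Grade 4, so the Grade 4 restart limit matters only if Appendix IV's restart option is kept. That is a separate question, not settled here.

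**What to change.** 1. State the same sentence in footnote 6 and in the Grade 3 and Grade 4 rows of D.1 and D.2: after any systolic >200 or diastolic >110, lenvatinib stays on hold until systolic is <150 and diastolic is ≤99. Leave the Principal Investigator and hypertension-specialist consultation rules and the dose-reduction rules unchanged. For Grade 3 pressures that never exceed 200 or 110, Appendix IV's ≤159/≤99 stays as it is. The systolic figure is footnote 6's own and matches the systolic entry limit in Section 3.18; the diastolic figure is Appendix IV's own, so no new threshold is introduced.
2. In the D.2 Grade 2 lenvatinib cell, replace Step 4 with Step 3.
3. Set Grade 1 diastolic to 80-89 in D.1 and D.2, so that 90 falls only in Grade 2.

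The cost is wording in two tables and one footnote, with no change to visits or data collection. The first change means a slightly longer hold for some patients, and that time counts toward the two-week limit after which protocol therapy ends.

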8.34 Management of Subjects with Elevations in AST, ALT and/or Bilirubin

Management of AST, ALT and/or Bilirubin Elevations	
Isolated AST/ALT elevations between 3X ULN and 8X ULN	Continue lenvatinib, but monitor weekly until AST/ALT returns to ≤ 2.5 or baseline
AST/ALT >8 X ULN	
Hold lenvatinib until AST/ALT returns to ≤ 2.5 X ULN or baseline
 
If the potential benefit of reinitiating lenvatinib treatment is considered to outweigh the risk for hepatotoxicity, then consider reintroducing lenvatinib at one dose level less and measure serum liver tests weekly for 8 weeks only after discussion with the PI
 
If AST/ALT elevations >3 X ULN recur, then lenvatinib should be permanently discontinued and patient enters event monitoring phase

AST/ALT >3 X ULN and	Discontinue lenvatinib and enter event monitoring phase

concurrent direct bilirubin elevations >2 X ULN	
Mild indirect hyperbilirubinemia, known or suspected Gilbert's syndrome, and elevation in ALT >3 X ULN	Continue lenvatinib, but monitor weekly until ALT returns to Grade 1 (NCI CTCAE v4) or baseline

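### The scheduled chemistry panel omits ALT, so a first ALT rise with AST below 3 X ULN cannot trigger the hold or stop rules in 8.34

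*Combined protocol and SAP*

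**What the plan says.** The Test Schedule in 4.1 has one chemistry panel, drawn within 14 days before registration, before Day 1 of each later cycle, and at end of treatment. Footnote 8 sets out its content by analyte: "AST, alk phos, total bilirubin (direct if TBili is elevated), creatinine", followed by calculated creatinine clearance, albumin, glucose, electrolytes and minerals, uric acid and LDH. ALT does not appear. The screening limits in 3.16 include AST and bilirubin, but not ALT.

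Section 8.34 sets the actions for liver abnormalities in four rows:

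- "Isolated AST/ALT elevations between 3X ULN and 8X ULN": "Continue lenvatinib, but monitor weekly until AST/ALT returns to" 2.5 or baseline.
- AST/ALT above 8 X ULN: "Hold lenvatinib until AST/ALT returns to" 2.5 X ULN or baseline. A restart is possible after discussion with the PI, by "reintroducing lenvatinib at one dose level less and measure serum liver tests weekly for 8 weeks". If values above 3 X ULN recur, "then lenvatinib should be permanently discontinued and patient enters event monitoring phase".
- AST/ALT above 3 X ULN with "concurrent direct bilirubin elevations >2 X ULN": discontinue.
- Mild indirect hyperbilirubinemia, known or suspected Gilbert's syndrome, and ALT above 3 X ULN: "Continue lenvatinib, but monitor weekly until ALT returns to Grade 1" or baseline.

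The nursing guideline 15.199 asks for liver function tests to be monitored, without naming analytes or time points.

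**The concern.** The plan makes dosing decisions depend on an analyte that it never schedules. A patient whose ALT first rises above 8 X ULN while AST stays below 3 X ULN should have lenvatinib held under 8.34, but would stay on drug as far as the scheduled tests show. The discontinuation rule has the same problem when ALT alone supplies its transaminase half. The panel gives direct bilirubin once total bilirubin is raised, so ALT is then the only missing input. There is also no required baseline ALT for the recovery criteria that allow a return to baseline.

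What is at stake is patient safety on a drug for which 15.17 lists raised ALT, acute hepatitis, liver injury and hepatic failure as known risks. The efficacy analysis is not at stake.

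**Working it through.** The plan gives no figure to reproduce here, so the check compares the analytes in footnote 8 with the trigger of each rule in 8.34.

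**Case examined:** a first ALT rise, AST below 3 X ULN, and only the scheduled panel available.

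| 8.34 row | Trigger | Available from the panel | What is lost |
|---|---|---|---|
| 3 to 8 X ULN | AST or ALT in range | AST, not in range | Weekly monitoring |
| Above 8 X ULN | AST or ALT above limit | AST, below limit | Hold |
| Above 3 X ULN with direct bilirubin above 2 X ULN | AST or ALT, plus bilirubin | AST, below limit; bilirubin | Discontinuation |
| Gilbert's | ALT above 3 X ULN | No ALT | Weekly monitoring (drug continues either way) |

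A dosing action is lost in 2 of 4 rows, and monitoring only in the other 2.

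**Why the case is limited to AST below 3 X ULN.** Once AST reaches 3 X ULN, the first row starts weekly AST/ALT monitoring, which brings ALT in. If AST itself exceeds 8 X ULN, or exceeds 3 X ULN with the bilirubin condition, the rule is met without ALT.

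**Why the case is limited to a first rise.** After a hold and restart, 8.34 requires weekly liver tests for 8 weeks: 8 × 7 = 56 days, and 56 / 28 = 2 cycles. If those tests include ALT, which 8.34 does not state, the gap after restart is an ALT-only recurrence beyond that period.

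**Scheduled panels.** By the start of cycle 6 there has been 1 at screening and 5 before cycles 2 to 6, so 1 + 5 = 6, with one more at end of treatment. None names ALT. With ALT on the panel, a first rise would be seen at the next draw, nominally within one 28-day cycle.

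**Other places that might supply ALT:**

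- 7.2, criteria for continuing treatment: no liver test.
- 10.61, adverse events graded at each evaluation: no liver item.
- 8.2, general rule for other non-hematologic events (hold at Grade 3, discontinue at Grade 4): for an ALT-only rise, it needs an ALT result first.
- 15.199: no analyte and no timing.

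**The case against.** The strongest reply is that this is a drafting slip with little practical effect. Footnote 8 ends in a trailing comma after LDH, so an item may have been lost. The title of 8.34 and the wording of 15.199 suggest that the authors assumed ALT would be available, and a routine laboratory panel may well report it. That may be true. But no section schedules ALT, 3.16 is AST-only as well, and labs may be done locally (4.1 footnote 3, 7.4, 7.5), so the written list is what tells an outside laboratory which tests to run. A lost item would itself be a reason to correct the footnote.

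Three further points trim the weight of the concern:

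- **Bilirubin backstop.** The general rule in 8.2 would act on a bilirubin rise of Grade 3 or 4 without ALT, and a raised direct bilirubin may lead a clinician to test ALT. This narrows the gap in the discontinuation row. It does not cover lower-grade bilirubin rises or an ALT-only rise.
- **Baseline ALT.** The recovery criteria also offer a fixed limit (2.5 X ULN, or Grade 1 in the Gilbert's row). A missing baseline matters only for a patient who entered above that limit.
- **Frequency.** 15.17 lists raised ALT among events below 1%, limited to important or life-threatening ones. Taken at face value for 25 patients, that is fewer than 0.01 × 25 = 0.25 expected. It is not a usable rate for threshold crossings, however: the same list includes proteinuria, which 1.233 reports in 31% of patients in the phase 3 trial. It does suggest that severe events would be few.

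**Conclusion.** The concern holds. As written, the schedule cannot trigger the 8.34 hold or discontinuation rule for a first ALT rise while AST is below 3 X ULN. Two of the four rows lose a dosing action and two lose weekly monitoring.

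The conclusion rests on reading footnote 8 as the complete panel and on judging the plan by its scheduled tests, not by what a site may do in addition. No event rate is claimed, because the documents give none for ALT crossing a limit without AST. It is a limited safety gap that should be closed; the response endpoint, the two-stage decision rule and the sample size are untouched.

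**What to change.** Add ALT to the analytes in footnote 8 of the Test Schedule at the panel's existing time points: screening, which supplies the baseline value, before each later cycle, and end of treatment. The thresholds in 8.34 and the AST-only eligibility limit in 3.16 can stay as they are. The cost is one more analyte on blood already drawn and a one-word protocol change, with no added visit. If sites already report ALT, the change only brings the protocol into line with practice.
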